1.0 Background

Obesity and its multitude of comorbidities represent a growing problem in the US and around the world. To date, dietary interventions have been largely unsuccessful in promoting prolonged weight loss, and many patients undergo medical and/or surgical approaches to lose weight and prevent obesityassociated diseases. Improved understanding of biochemical mechanisms in obesity and specific dietary factors that modulate obesity may have profound health benefits for millions of people. N-acyl-phosphatidylethanolamine (NAPEs) and their active metabolites, N-acyl-ethanolamides (NAEs) are lipid satiety factors that are normally biosynthesized in the intestinal tract in response to food intake(1, 2). While NAPEs are endogenously synthesized by mammals in their intestinal tract, many other organisms, including plants, also biosynthesize NAPEs. Reduced levels of NAPEs and NAEs have been found in obese humans and in response to chronic high fat diet(3), suggesting that increasing plasma NAPE and NAEs levels may be beneficial to obese individuals trying to lose weight or to keep off weight gain after losing weight.

The vast majority of studies on effects of diet on NAPE and NAE levels, and of the effects of these compounds on obesity and disease have been performed on rodent models; human studies are lacking. We have convincing evidence (see below in Preliminary Studies) that increasing plasma NAPEs, either by inducing bacteria-mediated NAPE production in the intestines or by direct IP injection, slows weight gain in mouse models of obesity(3). We therefore hypothesize that increasing plasma NAPE and NAE levels may induce satiety in human subjects, preventing weight gain and possibly improving weight loss in obese individuals.

To test this hypothesis, we need safe and reliable means of elevating plasma NAPEs in human subjects. As modulating bacterial expression of NAPEs in humans is not currently feasible, we sought dietary means to increase plasma NAPEs. As detailed below, we evaluated various foods as NAPE and NAE sources, and we found that oat bran has high levels of both. In mice, a single dose of oat bran was sufficient to raise plasma NAPE levels by approximately 50% over two hours. Thus, dietary oatmeal may be a safe and effective way to raise NAPE levels.

2.0 Rationale and Specific Aims

General Approach: In this pilot trial, we will study the effect of typical meal-sized doses of oatmeal on blood levels of NAPEs and their metabolites. Healthy volunteers will be fed a weight-based dose of oatmeal, and serial blood measurements will be collected to determine the subsequent change in serum NAPEs. From preliminary mouse data, we hypothesize that a 0.8g Oatmeal per kg mass (1-2 standard servings) will provide sufficient endogenous NAPE to double serum levels from baseline.

2.1 Rationale and Strategy

Patient population: The current study will help to establish the acute effects of moderate sized servings of oatmeal on serum NAPE levels. If successful, information gained in the current study will be used to study the effect of dietary changes on NAPEs in obese and lean individuals. Thus, we will exclude patients with obesity (BMI>or= 30) or other known metabolic diseases. We will also exclude patients with known gastrointestinal disorders that may affect absorption of nutrients.

Food choice: Based on our labs screen of various foods, we identified oatmeal as a valid source of NAPEs. Our prior studies in mice using synthetic NAPE and with bacteria biosynthesizing NAPE suggest that a dose of store-bought instant oatmeal sufficient to deliver 0.135 mg NAPE per kg body should be sufficient to double plasma NAE levels from baseline. For a 100 kg person, 80 grams of dry regular instant oatmeal (2 servings) provides this 0.135 mg / kg dose. (The dose of dry oatmeal per person = (body weight in kg / 100 kg)* 80 g dry oatmeal. Thus for 50 kg person, 40 g dry oatmeal (1 serving) provides the required dose.) Oatmeal will be served unsweetened only with water to control for confounding effects of any sweeteners or additives.

Study Duration: Our studies in mice show a peak in blood NAPE levels within 90 min following oatmeal consumption. We therefore expect that serial collection over two hours will be sufficient to detect change from baseline.

Choice of measurements: Mass spectroscopy is an efficient and reliable method to measure NAPEs and their metabolites. Our laboratory is experienced in mass spectrometry and has access to all necessary machines and reagents. We will also measure blood glucose in blood samples, as this is easily measurable and may be important clinically in future experiments.

2.2 Specific Aims

Obesity and its associated comorbidities are increasing in prevalence. Dietary or medical interventions to prevent and treat obesity have been only moderately effective and difficult for patients to implement. N-acyl-phosphatidylethanolamine (NAPEs) and their active metabolites, N-acyl-ethanolamides (NAEs) are lipid satiety factors that may play a role in losing weight and in maintaining weight loss.

Overarching Hypothesis: Pharmaceutical and dietary methods to increase NAPE levels will promote satiety and aid in non-surgical weight loss.

[figure not shown]
Specific Hypothesis: Our preliminary data have shown that oatmeal is rich in endogenous NAPEs, and a relatively modest serving of oatmeal leads to a doubling in NAPE and NAE levels in mice. We hypothesize that similar body-mass based serving of regular oatmeal will lead to a doubling of serum NAPE and NAE levels in humans.

Aim 1: To determine the acute effects of dietary oatmeal on serum levels of NAPEs and NAEs in humans. To meet this aim, we will serve 10 healthy subjects a weight-based serving of oatmeal while drawing blood serially over two hours. Serum NAPE and NAE levels will be measured by mass spectrometry.

3.0 Animal Studies and Previous Human Studies

Our lab has published results showing that administration of E. coli that are engineered to produce NAPEs attenuates high-fat diet induced obesity. We transformed C31-DE3 laboratory strain of E. coli with At1g78690, an *N*-acyltransferase from *Arabidopsis thaliana* that catalyzes the synthesis of NAPEs(4). These bacteria (pNAPE-EcN) were then administered to high-fat diet fed (HFD) C57BL6 mice via drinking water for 8 weeks, during which time food intake, weight gain, and body composition were monitored. pNAPE-EcN administration attenuated weight gain (Fig 1a), decreased fat mass (Fig 1b), and

attenuated post-prandial glucose excursions (Fig 1c). It also induced expression of genes encoding for fatty acid oxidation but not fatty acid synthesis and reduced expression of inflammatory genes in the liver (Fig 1d). Furthermore, it decreased serum cholesterol, inhibitied development and necrosis of atherosclerotic lesions, and inhibited development of fatty-liver disease (data not shown). See (5). **Fig 1a-d. pNAPE-EcN attenuates HFD-induced weight gain and fat mass, decreases post prandial blood glucose excursions, and induces expression of genes encoding for fatty acid oxidation but not fatty acid synthesis and reduces expression of inflammatory genes in the liver.**

Oral purified NAPE showed similar results with regards to weight gain, though the effects were far less potent than with use of pNAPE-EcN bacteria (Fig 2a vs 2b). We found that levels of NAPEs varies widely between different mouse diets (Fig 3), which led us to hypothesize that different dietary sources may be enriched in NAPEs compared to others. Fig 4 shows varying NAPE concentrations in various natural foods. Based on these results, we chose oatmeal as a potentially effective source of dietary NAPEs. When mice were fed a 0.8g/kg dose of dry oatmeal, we saw a 50% increase in plasma NAPE over the subsequent 2 hours, whereas feeding similar caloric amounts of applesauce had no such effect (Fig 5).

[figure not shown]

Fig 2a-b. Oral NAPE is less potent than pNAPE-EcN, even at high doses (200mg/kg).

Fig 3. NAPE levels vary widely by mouse diet.

[figure not shown]
[figure not shown]

Fig 4. NAPE content of various foods.

[figure not shown]

Fig 5. Effect of dietary oatmeal on plasma NAPE in mice.

4. Inclusion/Exclusion Criteria

There is no known effect of age, sex, or race on NAPE absorption, so we will enroll any interested patient who meets the following criteria:

Inclusion Criteria	Exclusion Criteria
• Age: ≥ 18 years	• BMI>30 or <20
• BMI: 20-30 kg/m ²	 History of type 1 or 2 diabetes
	 History of coronary artery disease
	 History of oatmeal allergies
	History of irritable bowel syndrome
	History of inflammatory bowel disease
	History of celiac disease
	 History of hyper/hypo-coagulability
	History of food intolerances
	 History of malabsorption

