5.0 Screening and Enrollment

Study participants will be recruited by word of mouth among colleagues and acquaintances of the study investigators. Given the low number of subjects, we anticipate that this will be sufficient. Subjects will meet initially with [name] for a medical history and physical to determine eligibility.

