6.0 Study Procedures

Participants will present after overnight fast to the CRC. They will have IV catheter inserted and baseline blood obtained (5ml). They will then be fed the above calculated dose of oatmeal, and blood will be drawn at 30, 60, 90, and 120 minutes (5ml each time). Blood glucose will be measured at each timepoint, and remaining blood will be taken to [name] lab for mass spectrometric analysis of NAPEs and NAEs. All samples and data will be deidentified at time of collection for participant confidentiality. Measures:

- -Bloodwork:
 - Glucose: POC glucose will be measured using clinical glucometer at time of blood sampling.
 - Serum NAPE and NAE levels: Samples will be centrifuged and serum NAPE and NAE levels measured by mass spectrometry in the [name] laboratory.
- Anthropometrics:
 - Height (m) and Weight (kg) measured on calibrated digital equipment will be used to calculate BMI.

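### Do Sections 2.1 and 4 disagree on who may be enrolled, at a BMI of exactly 30 and for metabolic disease other than diabetes?

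*Combined protocol and SAP*

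**What the plan says.** Section 2.1 (Rationale and Strategy) describes the intended population in prose: "we will exclude patients with obesity (BMI>or= 30) or other known metabolic diseases". It adds that people with gastrointestinal disorders that could affect absorption are excluded too.

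Section 4 (Inclusion/Exclusion Criteria) gives the working list and says of it: "There is no known effect of age, sex, or race on NAPE absorption, so we will enroll any interested patient who meets the following criteria". The inclusion side asks for adults with a BMI of 20 to 30. The exclusion side has 10 lines: BMI above 30 or below 20, diabetes ("History of type 1 or 2 diabetes"), coronary artery disease, oatmeal allergy, irritable bowel syndrome, inflammatory bowel disease, celiac disease, coagulation disorders, food intolerances and malabsorption. It has no catch-all line.

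Three other places bear on eligibility. Section 2.0 says "Healthy volunteers will be fed a weight-based dose of oatmeal" and Section 2.2 says "we will serve 10 healthy subjects a weight-based serving of oatmeal", neither defining healthy. Section 5.0 has each candidate seen "for a medical history and physical to determine eligibility". Section 6.0 says that height and weight "measured on calibrated digital equipment will be used to calculate BMI", with no rule on decimal places.

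**The concern.** Two sections of one protocol appear to set different entry rules. Section 2.1 is worded as a commitment, not as background. Section 4 says that anyone meeting its list will be enrolled, so whatever it leaves out is, on its face, allowed. A screener working from Section 4 could therefore enrol someone whom Section 2.1 rules out.

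At stake would be a clear description of the population and a clear answer to whether a given enrolment was a protocol deviation. In a study this small, each such person carries visible weight. The obesity boundary is also part of the study's rationale: Section 1.0 reports lower NAPE and NAE levels in obese people, and Section 2.1 keeps obese people out because obese and lean individuals are to be studied later.

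**Working it through.** The check is mainly textual. The plan states no figure to reproduce.

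**1. BMI at the boundary.**

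| BMI | Section 2.1 (excludes 30 or more) | Section 4 (includes 20 to 30, excludes above 30) | Agree? |
|---|---|---|---|
| just below 30 | admitted | admitted | yes |
| exactly 30 | excluded | admitted | no |
| just above 30 | excluded | excluded | yes |

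The range in Section 4 could be read loosely at its ends, but the paired exclusion of values above 30 shows that 30 itself is let in. The conflict is genuine and confined to one value.

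**2. How wide that value could be in practice.** BMI is calculated from measured height and weight. Unrounded, the conflict has no width. If BMI were rounded first, the affected range of body weight is the BMI width times height squared. Heights of 1.60, 1.75 and 1.90 m are assumptions, as is any rounding:

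- One decimal (29.95 to 30.05, width 0.1): 0.1 × 1.60² = 0.26 kg; 0.1 × 1.75² = 0.31 kg; 0.1 × 1.90² = 0.36 kg.
- Whole number (29.5 to 30.5, width 1.0): 1.0 × 1.60² = 2.56 kg; 1.0 × 1.75² = 3.06 kg; 1.0 × 1.90² = 3.61 kg.

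The documents describe no rounding, so these are outer illustrations and not the size of the problem.

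**3. Metabolic disease.** The wording of Section 2.1 treats obesity as itself a metabolic disease and then refers to others. On that reading Section 4 covers two: obesity, through the BMI line, and diabetes. The gap is a person with a known metabolic disease that is neither of these, and who also has none of the remaining listed conditions. Section 2.1 excludes that person; Section 4 does not mention them.

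This differs in kind from the BMI point. Section 2.1 also excludes gastrointestinal disorders as a category, and Section 4 turns that into named conditions. The metabolic category is treated the same way, only with a shorter list. A category carried over incompletely is not the same as two rules that contradict each other.

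**4. Effect on the result.** Section 10.0 compares each subject's NAPE and NAE levels with that subject's own baseline and tests the mean increase with a t test. There is no between-group comparison that an unusual subject could unbalance, and no BMI or disease term in the analysis. One subject is 1/10 = 10% of the sample. The documents do not show that a non-diabetic metabolic disease, or a BMI of 30 rather than just below it, changes the response to oatmeal. They also give no figure for how many volunteers either point would touch.

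**The case for a change.** The strongest argument for a change is that the inconsistency is certain and its cure costs two lines of text. Section 2.1 says what the investigators will do, and its gastrointestinal exclusion is carried into Section 4 more fully, including a broad malabsorption line, so the thinner metabolic entry looks like an omission. Healthy is undefined, and the screening visit applies criteria without adding any. An enrolment could then be called a deviation or not, depending on the section read.

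The textual part of this stands: the two sections do not match, and nothing elsewhere settles them formally. The practical part is weaker. Section 2.1 is a rationale paragraph and Section 4 is the criteria list, so it is reasonably plain which one a screener applies. Calling the subjects healthy and taking a medical history make it less likely, though not impossible, that someone with a known metabolic disease is enrolled. Reconciling the text would not necessarily alter conduct either: the documents do not show which version was intended, and narrowing Section 2.1 to match Section 4 would edit only the rationale.

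The point about lower levels in obese people concerns levels, whereas the analysis concerns change from each person's own level. It does not show that a person at exactly 30 responds differently from one just below, whom both sections admit.

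**Conclusion.** The mismatch is real but calls for no change to the plan. One part is a slip at a single boundary value; the other is a category in the rationale that the criteria list spells out incompletely. Using the Section 4 list as written gives a usable entry rule, and the within-subject comparison remains sound under it. A report that describes its subjects by the Section 4 criteria and their recorded characteristics would tell readers who was studied.

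The size is at most 10% of the sample for each affected subject, with no expected number that can be derived from the documents and no bias shown in either direction. This rests on two assumptions: that screening follows Section 4, and that BMI is used as calculated or rounded only finely. If BMI were rounded to a whole number, the boundary would widen to roughly 2.6 to 3.6 kg at the assumed heights, but the comparison with baseline would be unaffected. Aligning the sections would be tidy editing and would not change what the trial measures or can conclude.

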5.0 Screening and Enrollment

Study participants will be recruited by word of mouth among colleagues and acquaintances of the study investigators. Given the low number of subjects, we anticipate that this will be sufficient. Subjects will meet initially with [name] for a medical history and physical to determine eligibility.

6.0 Study Procedures

Participants will present after overnight fast to the CRC. They will have IV catheter inserted and baseline blood obtained (5ml). They will then be fed the above calculated dose of oatmeal, and blood will be drawn at 30, 60, 90, and 120 minutes (5ml each time). Blood glucose will be measured at each timepoint, and remaining blood will be taken to [name] lab for mass spectrometric analysis of NAPEs and NAEs. All samples and data will be deidentified at time of collection for participant confidentiality. Measures:

- -Bloodwork:
 - Glucose: POC glucose will be measured using clinical glucometer at time of blood sampling.
 - Serum NAPE and NAE levels: Samples will be centrifuged and serum NAPE and NAE levels measured by mass spectrometry in the [name] laboratory.
- Anthropometrics:
 - Height (m) and Weight (kg) measured on calibrated digital equipment will be used to calculate BMI.

7.0 Risks

- The participant will be required not to eat or drink, except water, after 10 pm on the night before testing visit. This may cause the participant to have a headache or a feeling of weakness, or the participant may become irritable.
- Blood draw: Blood draws can cause redness, soreness, bleeding or bruising at the needle stick site. The CRC nurses will be careful and use sterile technique. Sometimes people feel faint. The nurse may put some cream (called EMLA) on the skin to numb the area so the participant will not feel the needle stick as much. The numbing cream may make the skin change color, but this is rare.
- Patients may be allergic/intolerant to oatmeal or trace contaminants in oatmeal product.
- Risks that are not known: There are no known risks beyond those mentioned above. If new information is discovered that may affect the risks or benefits of this study, the participant will be told so that he/she can decide whether or not to remain in the study.

8.0 Reporting of Adverse Events or Unanticipated Problems involving Risk to Participants or Others All serious and unanticipated adverse events or problems involving risks to subjects that may possibly be or are known to be related to the research activity will be reported promptly to the IRB office per Vanderbilt University IRB Policy. The PI will ensure proper data and safety monitoring for the materials and data used for the purposes of this study.

9.0 Study Withdrawal/Discontinuation

Subjects may choose not to participate in this research study. This decision will not alter the routine care administered by the physician or the risks associated with standard of care procedures. Additionally, the participant will be removed from this study if the investigator does not think it is in best interest for the subject to be in this study. If the participant is removed from the study he/she will be told the reason why.

10.0 Statistical Considerations

Serum NAPE and NAE levels will be compared with each individuals baseline level, with statistical significance of mean increase over baseline determined by students t test.

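### The only planned analysis tests for any rise from baseline, so it cannot answer the doubling hypothesis, and the post-meal draw it uses is not named

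*Combined protocol and SAP*

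**What the plan says.** Section 10.0 is a single sentence. Levels are compared with each subject's own baseline, "with statistical significance of mean increase over baseline determined by students t test". The null value is not stated, but zero change is implied. Significance level, sidedness and expected variability are not given.

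The hypothesis is more specific than a rise:

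- Section 2.0 expects that the oatmeal dose "will provide sufficient endogenous NAPE to double serum levels from baseline".
- Section 2.2 says: "We hypothesize that similar body-mass based serving of regular oatmeal will lead to a doubling of serum NAPE and NAE levels in humans".

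On sampling, Section 6.0 states that "blood will be drawn at 30, 60, 90, and 120 minutes", after one baseline draw. Section 2.1 says: "Our studies in mice show a peak in blood NAPE levels within 90 min following oatmeal consumption". It uses this to justify two hours of sampling, not to choose a time point for analysis.

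The mouse results are described in two ways. Section 2.2 says that "a relatively modest serving of oatmeal leads to a doubling in NAPE and NAE levels in mice". Section 1.0 says that "a single dose of oat bran was sufficient to raise plasma NAPE levels by approximately 50% over two hours". Section 3.0, reporting on dry oatmeal at 0.8 g/kg, says "we saw a 50% increase in plasma NAPE over the subsequent 2 hours".

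**The concern.** There are two gaps.

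**The test and the hypothesis do not match.** A test of zero change suits Aim 1, which asks about acute effects in general. It does not address a factor of 2. The mean increase is computed along the way, but without an interval nobody can say whether it is compatible with doubling. The distinction matters here, because the documents' own mouse figures include both a doubling and a rise of about 50%. A real rise short of doubling is a realistic result, and the planned test would give it the same label as a doubling.

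**The comparison is undefined.** If levels peak and then fall, a doubling at one time and a doubling averaged over two hours are different claims. With four draws and none named, the comparison can be chosen after the levels are known.

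**Working it through.** **Inputs from the documents.** 10 subjects (Section 2.2, Aim 1); hypothesised fold change 2 (Sections 2.0 and 2.2); contrasting fold change 1.5 (Sections 1.0 and 3.0); four post-meal draws and one baseline draw (Section 6.0).

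**Assumptions.** Two-sided 0.05, and every SD and CV below. The documents give none of these, so the sample size of 10 cannot be reproduced.

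**Step 1: when the planned test is significant.** A paired t test on 10 subjects has 9 degrees of freedom and t(0.975, 9) = 2.262. The mean rise is significant when it exceeds 2.262/√10 = 0.715 SD of change. The 95% interval is the mean ± 0.715 SD.

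| SD of change (% of baseline) | Observed mean rise | p | 95% interval |
|---|---|---|---|
| 50% | +50% | 0.012 | +14% to +86% |
| 50% | +100% | 0.00014 | +64% to +136% |
| 75% | +50% | 0.064 | −4% to +104% |

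The first two rows are both significant, yet only the first excludes a doubling. The third is not significant, yet does not exclude a doubling.

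**Step 2: how well significance separates 1.5-fold from 2-fold.** The probability of a significant rise comes from the noncentral t distribution with noncentrality √10 × (true rise)/SD, using the same SD for both true rises.

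| SD of change | True +50% | True +100% | Ratio |
|---|---|---|---|
| 30% | 99.6% | 100% | 1.0 |
| 50% | 80% | 100% | 1.2 |
| 70% | 52% | 98% | 1.9 |
| 100% | 29% | 80% | 2.7 |

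The ratio is the factor by which a significant result favours doubling over a 50% rise. It is close to 1 where the test is most sensitive.

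**Step 3: leaving the draw unnamed.** With no true change, one named draw shows a significant rise in 2.5% of trials. If each of four draws is tested against the shared baseline, at least one shows a rise in about 8% (simulation, independent draws). Equal correlation of 0.5 among all five draws leaves this at about 8%.

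**Step 4: what an interval on the fold change would give.** Work with log ratios. Let sw = √ln(1 + CV²), where CV is within-person, and let τ be the between-person SD of response on the log scale. The SD of the log ratio is √(k·sw² + τ²), with k = 2 for one draw and k = 1.25 for the mean of four independent draws. The chance that the upper limit falls below 2 when the truth is 1.5 uses noncentrality √10 × ln(2/1.5)/SD. For one draw at CV 30% and τ = 0: sw = 0.294, SD = 0.415, noncentrality = 3.162 × 0.288/0.415 = 2.19, chance = 50%.

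| Within-person CV | τ = 0: one draw / mean of four | τ = 0.3: one draw / mean of four |
|---|---|---|
| 20% | 82% / 95% | 51% / 59% |
| 30% | 50% / 70% | 36% / 45% |
| 40% | 32% / 47% | 26% / 34% |

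The interval can therefore exclude doubling in a useful share of trials if variability is low, and less often if people respond differently.

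**The case against.** The strongest reply is that this is a 10-subject pilot. Aim 1 asks about acute effects, Section 2.1 speaks of detecting change from baseline, and no section sets a decision rule at 2-fold. The paired test is sound for that purpose, and a confidence interval needs only the mean, SD and sample size already in hand, so the first gap could be called one of reporting. That is fair as to the test itself. But doubling is the stated hypothesis, and no planned output answers it.

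The gain at this sample size is also limited. A true rise of exactly 2 gives an interval that includes 2 in 95% of trials, so doubling would rarely be confirmed. This stands, and the interval at least shows that uncertainty.

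The mouse statements may not describe one experiment. Section 1.0 concerns oat bran, Section 3.0 dry oatmeal at a stated dose, and Section 2.2 gives no dose. A doubling at peak and a 50% rise over two hours could also both be true. This softens the contradiction, but it makes naming the time point or summary more important.

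Finally, the log scale is a choice. An interval on the percentage change, read against +100%, would also address doubling. Nothing in this reply supplies the missing draw or summary, which is the harder gap to defend.

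**Conclusion.** The concern holds on both counts. Followed as written, the plan yields a p-value against zero change that cannot confirm or exclude a doubling, and it leaves open which post-meal level is compared. This conclusion comes from the wording and needs no assumed variability. The sizes do rest on assumptions: at SDs of change from 30% to 100% of baseline, a significant result favours doubling over a 50% rise by a factor of only 1.0 to 2.7, and free choice among four draws raises the false-rise rate from 2.5% to about 8%. The trial would remain interpretable for any rise, so this should be fixed but is not fatal.

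**What to change.** Before any post-meal level is seen, decide which doubling is meant. Name one time point, or one summary such as the mean of the four log levels. Then replace the sentence in Section 10.0 with text such as:

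> Separately for NAPE and for NAE, the geometric mean fold change over baseline at [named time point or summary] is reported with a two-sided 95% confidence interval from a paired t analysis of log ratios. A rise is concluded if the lower limit is above 1. We state whether the interval excludes or includes 2, for this [time point or summary] only. Fold changes with 95% confidence intervals at the other time points are descriptive.

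Either name one analyte as primary or accept that two tests carry an upward error of up to 1 − 0.975² = 4.9% if independent. Do not use each subject's highest draw: with independent draws at CV 30% it shows a 1.35-fold rise when there is none, and the t test calls that significant in 66% of trials. The mouse statements in Sections 1.0, 2.2 and 3.0 should be reconciled.

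The cost is one paragraph, with no new data or visits. The downsides are:

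- **Scale.** The log ratio can lose power if the response is additive. In simulation with normally distributed individual rises (mean and SD both 50% of mean baseline), power was about 81–83% for the absolute difference and 59–67% for the log ratio. With a proportional 1.5-fold response the order reversed (67% and 78%).
- **Averaging.** A four-draw mean dilutes a brief peak. An assumed profile of 1.2, 1.6, 2.0, 1.6 averages (1.2 × 1.6 × 2.0 × 1.6)^¼ = 1.57-fold. Its interval excludes 2 in 86%, 54% and 35% of trials at CV 20%, 30% and 40% (44%, 33% and 25% with τ = 0.3), although levels double at 90 minutes.
- **Precision.** Over the same CVs, the interval lies wholly above 2 only at an observed fold change of at least 2.3 to 3.0 (2.6 to 3.1 with τ = 0.3). It lies wholly below 2 only at 1.35–1.71 or less (1.28–1.53 or less).
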